8.1.4. Additional Reporting Requirements

Occurrences of events of overdose, drug misuse and drug abuse are considered “important medical events” that should also be reported within 24 hours using the appropriate reporting form. These events should be reported regardless of their association with other adverse events or serious adverse events.

Abuse of a medicinal product: Persistent or sporadic, intentional excessive use of medicinal products which is accompanied by harmful physical or psychological effects [DIR 2001/83/EC Art 1(16)].

Medication error: Refers to any unintended error in the prescribing, dispensing or administration of a medicinal product while in the control of the healthcare professional,

patient or consumer. Medication errors are an important cause of morbidity and mortality and many could be prevented or mitigated. They can fall broadly into 4 categories:

1. Wrong medication.
2. Wrong dose (including strength, form, timing, concentration, infusion rate and amount).
3. Wrong route of administration.
4. Wrong patient.

Occurrences of medication errors in a study subject should be reported within 24 hours using the Medication Error/Overdose form. In cases where a medication error results in a serious adverse event, the Serious Adverse Event reporting form should be used to report the SAE. Non-serious AEs associated with medication errors should be reported in AE page in eCRF.

Misuse: Intentional and inappropriate use of a medicinal product/device not in accordance with the prescribed or authorized dose, route of administration, and/or the indication(s) or not within the legal status of its supply (e.g., without prescription for medicinal products subject to medical prescription).

Overdose: Administration of a quantity of a medicinal product given per administration or per day which is above the maximum recommended dose according to the reference safety information for the investigational product or comparator as applicable. This also takes into account cumulative effects due to overdose.

8.1.5. Adverse Event of Special Interest (AESIs)

An adverse event of special interest (serious or non-serious) is one of scientific and medical concern specific to the Sponsor's product or program, which warrants ongoing monitoring and rapid communication by the investigator to the Sponsor (Section 8.6).

8.1.6. Complications of the Disease Under Study

Certain symptoms are considered typical outcomes following surgery and thus are expected side effects. Clinical events that are considered standard post-operative occurrences will be reported as AEs if they are considered untoward or unfavorable. In cases where the event is not considered as untoward or unfavorable it must be recorded as such in the source document. Consistency in reporting adverse events from all participating sites will be ensured through appropriate training and monitoring and investigators will be required to report all untoward or unfavorable events as adverse events based on their clinical judgment.

8.2. PROCEDURE FOR NON-SERIOUS ADVERSE EVENT RECORDING

All non-serious AEs that occur during the designated study period from consent up to EOS visit (Day 30 ± 7 days) following study drug administration must be assessed and recorded on the source documents and eCRF regardless of causal relationship to the study drug.

Study participation ends after the Day 30 visit. However, should a subject return to the investigator between Day 30 and Day 90 for routine follow-up visits (not scheduled for the purpose of the study), the investigator will record any update in the subject's safety information and report such information to the Sponsor using the data collection forms provided.

8.3. PROCEDURE FOR SERIOUS ADVERSE EVENT REPORTING

All SAEs involving the study biologics, the reportable malfunctions, serious injuries, death and incidents involving the biologic-application devices that occur during the designated study period from consent up to 90 days following study drug administration must be reported to Mallinckrodt Pharmaceutical's Global Pharmacovigilance Department (GPV) within 24 hours of awareness of the event using the provided study specific SAE/AESI Report Form and Device Reporting Form, respectively. The completion and processing of the Reporting Forms should follow the instructions in the provided Report Form completion guidelines. In addition to completing the Report Forms, each SAE/AESI, Medical Device Reporting (MDR) reportable malfunction, serious injury, death or Medical Device Vigilance (MDV) incident must be entered on the appropriate page of the CRF.

When death occurs due to a SAE, the cause of death must be reported as the SAE. The outcome of the causal SAE should be designated as "fatal."

The investigator must assess the causality for each SAE and incident.

The Sponsor or its representative will contact the investigator, if necessary, to clarify any of the event information. The investigator should provide any follow-up information for the event to the Sponsor on an SAE/AESI Report Form or a Device Reporting Form as soon as it becomes available.

If the investigator becomes aware of a SAE that occurs post-study period, that he or she wishes to report to the Sponsor (e.g., an event suspected to be causally related to the study biologics or the application devices), the event should be reported through the process described above as soon as possible.

Where appropriate, if required by local regulations or procedures, the investigator should report these events to the Institutional Review Board (IRB)/Ethics Committee (EC) and/or appropriate regulatory authority in addition to the Sponsor.

8.4. PROCEDURE FOR MEDICATION ERROR REPORTING

Medication errors with or without an AE should be recorded as medication errors in the eCRF as described in Section 8.2.

Medication errors with a SAE should be recorded as medication errors in the eCRF and reported to the Sponsor Pharmacovigilance Department as described in Section 8.3.

A missing dose (refer to Section 12.3) should be reported as a medication error if it was an “unintended error” as defined in Section 8.1.4.

8.5. PROCEDURE FOR ADVERSE DEVICE EFFECTS (ADES) REPORTING

Any AE related to the use of an investigational medical device should be reported within 24 hours using the Device Incident Report Form. In cases where an ADE occurs with a Serious Adverse Event, the SAE/AESI Report Form should be used to report the SAE and the Device Report Form should be used to report the ADE. When an ADE occurs without any concurrent SAE, the Device Report Form may be submitted alone.

8.6. ADVERSE EVENTS OF SPECIAL INTEREST

The AESI(s) listed below have been identified for the study product(s) in this protocol. Non-serious AESIs should be reported from the site to the sponsor within 72 hours and serious AESIs should be reported from the site to the sponsor within 24 hours. In both instances, the reporting procedure provided in Section 8.3 should be followed. The SAE/AESI Report Form, along with a targeted questionnaire when applicable, should be utilized for reporting the AESI even if a serious outcome may not apply. The SAE/AESI report form should indicate that the reported event is an AESI.

AESIs for this study product/protocol are as follows:

- Surgical site-related events, which includes inflammation, pain, foreign body reaction, and infection suggestive of a higher complication rate.
- Thromboembolic events, which includes acute ischemic events like pulmonary embolism, myocardial infarction, deep vein thrombosis and stroke.
- Re-bleeding at the TBS, including post-procedural hemorrhage, hematomas and compression/obstruction of the adjacent structures secondary to the hematomas.
- Air emboli-associated events, which includes acute respiratory failure or cardiovascular collapse occurring intra-operatively during or following the use of the RaplixaSpray device.
 - Additional information will be collected for events of potential air/gas emboli using the Raplixa Air or Gas Embolism Adverse Events questionnaire.

- Blood-borne pathogenic diseases such as hepatitis/HIV infection or prion disease suggestive of viral or prion transmission from Raplixa.

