5.5. CONCOMITANT MEDICATIONS

Subjects may continue all normally prescribed medication regimens during this trial, and must notify the investigator when changes are made to their medication regimens. Medications will be coded using the WHO drug dictionary.

5.5.1. **Rescue Treatment**

If hemostasis is not achieved TBS during the 5-minute TTH assessment period, administration of additional study drug (no more than 2 vials of Raplixa [2.0 g] total), or other topical hemostats are permitted. If hemostasis cannot be achieved at an OBS or Raplixa is not indicated for use at the OBS, rescue treatment, if needed, should follow a tiered approach:

1. Additional study drug or surgical hemostatic measures (e.g., suture, cautery, and ligature) should be considered first.
2. Followed by thrombin-free topical hemostats.
3. Finally, thrombin-containing hemostats (recombinant or human plasma-derived products) may be administered, if needed.

A list of examples of thrombin-free and thrombin-containing hemostatic agents is provided in Table 2.

Table 2: Examples of Other Topical Hemostatic Agents

Thrombin-Free	Thrombin-Containing ^a
CoSeal™	CoStasis®/Vitage®/TM
Surgifoam™	Crosseal™
Ultrafoam™	Tisseel®
Gelfoam®	Fibrin sealant produced by the blood bank or in the operating room
Instat™	Evicle™
BioGlue®	Evithrom™
DuraSeal®	Recothrom®
Bone wax®	Surgiflo®
	Tachosil®
	Artiss®

a. Investigators should consider the use of products containing thrombin, only after other rescue alternatives fail.

5.6. **BLINDING**

Subjects will be randomized in a single-blinded manner. Randomization will be done in a 2:1 ratio (active:control).

5.6.1. **Blinding of Study Medications**

Study drugs will be blinded to study subjects but not to the Investigators, the study site personnel, or the Sponsor's study team.

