10.4.3.1. Adverse Events

Adverse events (AE) will be coded using the Medical Dictionary for Regulatory Activities (MedDRA) dictionary. An AE (classified as preferred term) occurring during the study will be counted as a treatment emergent AE (TEAE) when it is not present at baseline or present at baseline but increased in severity after the initiation of study drug.

Summaries of the number and percentage of subjects with at least one SAE, MDR reportable events (malfunction, serious injury, or death), or MDV incident, and the number and percentage of subjects with at least one Grade 3, 4, or 5 AE, classified by MedDRA preferred term and system organ class, will be provided.

Adverse events of special interest as listed below will be summarized by treatment group. Details of the AEs of special interest are in Section 8.6:

- Surgical site-related events.
- Thromboembolic events.
- Re-bleeding at the bleeding sites.
- Gas embolism events.
- Blood borne pathogenic diseases suggestive of pathogen transmission from Raplixa.

Listings will be presented for subjects with SAEs/AEs leading to a treatment discontinuation or death.

The estimated rate of immunogenicity will be reported for both treatment arms. No immunogenicity data will be collected for, or reported on, children less than 6 months of age.

10.4.3.2. *Laboratory Tests*

Laboratory values will be summarized by treatment group, including changes and percentages of changes from baseline at each time point. Shift tables summarizing the counts and percentages of subjects who were normal at baseline, but became abnormal subsequently will be provided.

10.4.3.3. *Vital Signs*

Change and percent change from baseline in vital signs will be summarized descriptively at each scheduled time point by treatment group.

10.4.4. *Efficacy Analysis*

10.4.4.1. *Primary Efficacy Endpoints*

The primary efficacy endpoint is:

- Proportion of subjects who reach hemostasis at the first identified TBS within 4 minutes of study drug application.

If a subject achieves hemostasis at any point within 4 minutes of study drug application, they will be considered a “success”. All other subjects will be considered a “failure”.

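### Of five AESI categories to be summarized by arm, one cannot be met by a control subject, a second cannot if read literally, and a third rests on an undefined judgement by unblinded investigators

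*Combined protocol and SAP*

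**What the plan says.** Section 10.4.3.1 states: "Adverse events of special interest as listed below will be summarized by treatment group". It lists five short labels and sends the reader to Section 8.6 for the details. Section 8.6 defines the categories as follows.

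- Surgical site: "Surgical site-related events, which includes inflammation, pain, foreign body reaction, and infection suggestive of a higher complication rate". No criterion is given for the closing words, "infection suggestive of a higher complication rate".
- Thromboembolic: "Thromboembolic events, which includes acute ischemic events like pulmonary embolism, myocardial infarction, deep vein thrombosis and stroke".
- Re-bleeding: "Re-bleeding at the TBS, including post-procedural hemorrhage, hematomas and compression/obstruction of the adjacent structures secondary to the hematomas".
- Air emboli: a category said to include "acute respiratory failure or cardiovascular collapse occurring intra-operatively during or following the use of the RaplixaSpray device".
- Blood-borne disease: hepatitis, HIV or prion disease "suggestive of viral or prion transmission from Raplixa". The label in 10.4.3.1 repeats the link to Raplixa.

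Section 5.6.1 says who knows the assignment: "Study drugs will be blinded to study subjects but not to the Investigators". The same sentence adds site personnel and the sponsor's study team. Section 10.3.2.2 classifies subjects in the safety population by treatment actually received. Section 8.2 requires non-serious adverse events to be recorded whatever their cause.

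**The concern.** A by-arm safety table is informative only if the same clinical event would be counted in either arm. The control column supplies the background rate against which the active column is read. Some of these AESIs need that background. Intra-operative respiratory failure and cardiovascular collapse are non-specific. Blood-borne infection has other possible sources in both arms: transfusion is tracked as an endpoint (3.3), and rescue may include human plasma-derived thrombin (5.5.1).

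If a definition excludes control subjects, their count is zero whatever happens to them, and any imbalance can only run against Raplixa plus gelatin sponge (R+G). If a definition rests on an unstated criterion applied by someone who knows the arm, the two columns may have been filled by different standards, and the table cannot show whether they were.

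**Working it through.** **The plan's own figures.** The documents give no expected AESI rate, so there is no AESI figure to reproduce. The only design calculation is the power statement in 10.1, from which this point takes the arm sizes alone (58 R+G, 29 gelatin alone, G). It reproduces. The pooled proportion is (58 × 0.87 + 29 × 0.60)/87 = 0.78. The null standard error is √[0.78 × 0.22 × (1/58 + 1/29)] = 0.0942, and the alternative standard error is √[0.87 × 0.13/58 + 0.60 × 0.40/29] = 0.1011. Then z = (0.27 − 1.96 × 0.0942)/0.1011 ≈ 0.844, which gives power of 80.07% against a stated value of about 80%.

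**The five definitions side by side.** A G subject in the safety tables is one who did not receive Raplixa (10.3.2.2).

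| Category | Condition in 8.6 | Label in 10.4.3.1 | Can a G subject qualify? |
|---|---|---|---|
| Surgical site | Undefined phrase about complication rate; names no arm | Phrase omitted | Yes, by judgement |
| Thromboembolic | None | Same | Yes |
| Re-bleeding | Located at the target bleeding site (TBS) | At the bleeding sites generally | Yes |
| Air emboli | Examples tied to RaplixaSpray use (exposure and timing, not causality) | Gas embolism events, no device condition | Not if 8.6 is literal; possibly under the 10.4.3.1 label |
| Blood-borne | Suspected transmission from Raplixa | Raplixa link repeated | No |

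So one category is closed to controls, one is closed on a literal reading, one is open but subjective, and two are arm-neutral.

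**Categories closed to controls.** Suppose the same clinical event has true risk r in both arms. The values of r are assumptions. Expected events are 58r in R+G and 29r in G, but the G events are not counted.

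| r | R+G expected (58r) | G occurring but uncounted (29r) |
|---|---|---|
| 1% | 0.58 | 0.29 |
| 2% | 1.16 | 0.58 |
| 5% | 2.9 | 1.45 |
| 10% | 5.8 | 2.9 |

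The R+G column assumes that every such event qualifies. For air emboli only device-treated subjects can qualify, and 5.1.1 also allows application straight from the vial.

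**Surgical-site category.** Let every qualifying R+G event be flagged and let a fraction s of G events be flagged. With equal true risk r, the apparent ratio is r/(r × s) = 1/s.

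- s = 1.0: ratio 1.0
- s = 0.8: ratio 1.25
- s = 0.5: ratio 2.0 (for example 10% against 5% when r = 10%)

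The values of s, and the assumption that under-flagging falls on G, are illustrative. The grammar also leaves open whether the phrase qualifies infection only or all four terms. If it covers pain, it decides which of many routine events count: 1.1.2 reports post-operative pain among the adverse events seen in more than 10% of Raplixa subjects in the adult Phase 2 trials.

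**Do other planned tables fill the gap?** The preferred-term summaries named in 10.4.3.1 cover serious events, device-reportable events and Grade 3 to 5 events. Serious or high-grade collapse or infection would ordinarily appear there in both arms. No by-arm table of Grade 1 or 2 surgical-site events is specified, although 10.3.1 makes a general promise to summarize or list all data by arm.

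**The case against.** The strongest reply is that the affected part is small and the AESI list has another purpose.

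- Section 8.1.5 defines an AESI as a product-specific concern needing rapid communication to the sponsor. A zero for Raplixa-transmitted disease in subjects never given Raplixa explains itself. This stands as a reason to leave site reporting alone. It does not make the row useful in a by-arm table.
- The air-emboli wording follows a non-exhaustive verb, and 10.4.3.1 speaks only of gas embolism events, so an actual gas embolism in a control subject might be counted. This stands: that zero depends on the reading, and the two sections need to agree.
- The summary is descriptive, with no test, estimate or decision rule. This also stands. The language about comparison with Gelfoam is found only in the summary of a past amendment and is not relied on here.
- Section 10 refers to a separate SAP for detailed specifications. No separate SAP text is in the document supplied, so a term list may exist there and could not be checked.
- Lower-grade events are recorded in both arms, so the data are not lost. True, and that is why the remedy is cheap.

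A reader might infer that all AESI definitions require attribution to the product, so that the whole AESI summary is biased by construction. The documents do not support that. Thromboembolic events and TBS re-bleeding carry no such condition. The air-emboli condition concerns exposure and timing, not causality. The surgical-site phrase names no arm and can be met by a control subject.

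**Conclusion.** The point holds for three of the five categories, to different degrees. Blood-borne disease has a control count of zero by definition. Air emboli does too if the device condition in 8.6 is applied literally. Surgical-site events depend on a judgement that has no stated comparator or threshold and is made by investigators who know the arm, so bias is possible but not built in. By-arm counts for these categories cannot be read as comparable risks. The other two categories are unaffected.

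The documents do not allow the size of the distortion to be derived. The apparent ratios of 1.0 to 2.0 rest entirely on assumed flagging rates, and nothing in the documents establishes the direction of any differential flagging. The primary efficacy analysis and the sample size are untouched. The conclusion assumes that no arm-neutral AESI term list exists in the separate SAP.

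**What to change.** In 10.4.3.1, build the by-arm AESI tables from a MedDRA preferred-term list for each category. Fix the list before results are seen, which matters because the sponsor's team is unblinded. Apply it to all adverse events in both arms, regardless of investigator flag or attribution. For tabulation only:

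- drop the Raplixa-transmission condition and the complication-rate phrase;
- count gas-embolism events irrespective of device use, and include the respiratory-failure and cardiovascular-collapse terms;
- show product or device attribution in separate rows;
- reconcile the re-bleeding category, which is confined to the TBS in 8.6 but covers bleeding sites generally in 10.4.3.1.

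Leave the site reporting duties in 8.6 as they are. A split of R+G by spray or vial application is optional. It would be descriptive only, since the subgroups are not randomized and share about 58 subjects.

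The cost is a term list and some programming on events already recorded and MedDRA-coded. The downside is broader, less specific counts, which the separate attribution rows partly offset.

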8.7. REPORTING EVENTS OF PREGNANCY/LACTATION

Occurrences of pregnancy/lactation exposure in a study subject or study subject's partner should also be reported within 24 hours using the Pregnancy Reporting form. In cases where a pregnancy occurs with a Serious Adverse Event, the SAE/AESI Report form should be used to report the SAE and the Pregnancy Reporting form should be used to report the pregnancy. When a pregnancy occurs without any concurrent SAE, the Pregnancy Reporting form may be submitted alone. The pregnancy must be followed through to outcome of pregnancy. Any pregnancy discovered from the time of consent to follow-up must be reported.

8.8. POTENTIAL SAFETY UPDATES WITHIN 90 DAYS OF STUDY PRODUCT APPLICATION

Study participation ends after the Day 30 visit. However, should a subject return to the investigator between Day 30 and Day 90 for routine follow-up visits (not scheduled for the purpose of the study), the investigator will record any update in the subject's safety information and report such information to the Sponsor using the data collection forms provided.

9. DATA COLLECTION

An electronic data capture (EDC) system will be used for this trial. All users will be trained on the technical features of the EDC as well as the content of the eCRF by qualified personnel prior to gaining access to the EDC. A User ID/Password will be granted after training. This ID is not to be shared amongst the study staff. All users must have a unique account to enter or review data. The eCRF should be filled out by the site within 48 hours after a visit. It is not expected that the eCRF will serve as source for any data collected in this trial. If there is a reason for a site to do so, it must be approved by MDCO and documented in the site files.

Prior to the database being locked, the investigator or designee will review, approve and sign/date each completed eCRF. This signature serves as attestation of the Investigator's responsibility for ensuring that all data entered into the eCRF are complete, accurate and authentic. After the end of the trial, a copy of the data will be provided to the site. This copy will contain the final data, an audit trail of activity on the data, and any queries and answers that were posted for data clarification.

A second data lock date will be set to ensure the capture of safety data from routine or unspecified visits after the Day 30 visit but before Day 90.

